3. Accordingly, the theoretical framework for this study will be to use NF as a strategy and potential tool in relapse prevention. Negative emotional states, such as anger, anxiety, depression, frustration, and restlessness are associated with higher rate of relapse to drug use [20]. By closely monitoring these variables throughout the project, we will be able to assess whether NF has a potential add-on effect on the patient's ability to cope with such negative emotions and the ensuing drug urge and cravings.

4. The proposed design has a stronger user involvement than previous research efforts in the field. User representatives with personal experience with NF will take an active part in the intervention and have regular dialogue meetings with participants, allowing informal exchanges about the method (e.g., possible effects and side-effects). We expect this element of the study to potentially boost the effect of the intervention. This way of boosting effects of other interventions has recently become a recommended strategy in the addiction treatment field [21].

Approaches, hypotheses, and choice of method

The overall aim of the study is to acquire more knowledge about the effectiveness of NF in the treatment of substance use disorders in general, specifically in relation to its effect on physical and psychological distress (e.g. sleep disturbances, anxiety symptoms etc.), and subsequently on its ability to improve QoL and prevent relapse. An RCT study will be undertaken to examine whether neurofeedback (NF) + treatment as usual (TAU) compared to TAU only can increase the QoL of patients with a SUD in the short and long term. We hypothesized that, compared to the TAU condition the NF + TAU condition would result in higher QoL at the end of treatment as well as at a 3- and 12-month follow-up. Included in our QoL assessment measure is perceived functioning in important areas such as work and social relations.

Our secondary outcome hypothesis is that the NF+TAU condition will result in better substance use outcomes as well as improvement in sleep quality, psychological distress, and symptoms of anxiety and depression at the end of treatment and at follow-up compared to controls. Drop-out rates will also be compared for the two groups, controlling for baseline demographic and severity variables.

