In addition to the RCT, the project group will write up on an extended naturalistic cohort study initiated after the previous pilot, and investigate this cohort in relation to similar aims as described above.

Inclusion criteria

Patients with a substance use disorder referred to outpatient addiction treatment, aged >18 of both genders.

Exclusion criteria

Severe psychiatric disorders (e.g. psychosis) that have not been stabilized with e.g., medication (assessed as a part of the clinical process at the clinic). Severe cognitive impairment or language problems (inability to converse for interviews).

Experimental design

The proposed experimental study will have a two-group pre-post design with an intervention group (NF+TAU) and a control group (TAU). Participants will include patients referred to outpatient addiction treatment at two clinics within Sørlandet Hospital HF, in Kristiansand and in Arendal. Because regular attendance is desirable for participation in the project, certain clinical selection criteria will apply, but this will be handled not by the project group itself, rather it will reflect ordinary practice within the present clinical setting. Thus, patients are thought to be clinically eligible to the NF condition after having achieved an initial level of stable attendance at the clinic. This is congruent with the study's focus on relapse prevention.

Patients meeting the criteria for inclusion will be informed about the project and given the opportunity to participate. After providing written, informed consent, those patients who choose to participate will be randomly assigned to either NF training + TAU, or TAU alone. The allocation will be determined through notes prepared in sealed envelopes by an external researcher based on a block randomization design. As a part of the NF+TAU condition, participants will be invited to an informal dialogue session within a month of starting the intervention, in which a user representative will be available to answer potential questions and share individual experience concerning the treatment. The TAU participants will receive standard psychotherapeutic treatment, chosen according to individual needs and therapist preference.

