The intervention will consist of 20 sessions of symptom-based NF tailored to the individual patient. Training will be conducted using the Othmer method of NF from EEGinfo, comprising bipolar, infra-low frequency training, with the inclusion of synchrony and alfa-/theta training as needed.

All participants will complete the inventory described below at the outset. The instruments are chosen for their ability to measure internal states associated with a risk of triggering urges and cravings leading to drug use. Cognitive function is assessed because impairment in this domain is associated with poorer treatment outcomes, including decreased treatment retention in SUD patients [22]. QEEG data will be recorded prior to and after the 5 months intervention period. These data will be analyzed by our cooperating partner at Norwegian University of Science and Technology (NTNU) to identify possible biomarkers for addiction, and to study the neurophysiological effects of neurofeedback.

Instruments

In addition to basic demographics and the Mini International Neuropsychiatric Interview (M.I.N.I.) to confirm the SUD diagnosis [23], the inventory includes the items and scales below:

Primary outcome

- Quality of life, measured with
 - QoL-10, a 10-item questionnaire which rates the patient's subjective experience of life quality. The respondents are asked to rate their physical and psychological health as well as the quality of their relationships on five-point Likert scales. The scale also includes a subscale about perceived functioning in areas such as work, sexual and social relations [24].

Secondary outcomes

- Perceived functioning/well-being:
 - Outcome Rating Scale (ORS), a visual analogue scale consisting of four subscales measuring the patient's perceived functioning in the personal, interpersonal and social domains, in addition to a general measure of his or her perceived QoL. The respondents are asked to rate their perceived functioning in these areas from very low to very high on a 10 cm, unmarked horizontal line [25]. This scale was included to corroborate on the measurement of perceived functioning in

the QoL-10 functioning subscale and to be used in the repeated measuring of perceived functioning to assess trajectories of change (see below).

- Negative affect:

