- To assess the *trajectories of change* in the NF-TAU condition, a simple computer-based screening test will be administered weekly to each participant during the project period, measuring: a) alcohol and drug use, b) sleep quality, c) restlessness and trepidation and d) perceived functioning (ORS). These VAS scales have been described above.

The participants will be reassessed after treatment and at a 3- and 12- month follow-up period. Research assistants (RAs) blinded to the patient’s condition assignment will conduct the follow-up interviews. Efforts will also be made to examine non-completers. Respondents will be reimbursed NOK 250 (\$30) for completing the follow-up interviews.

Sample size calculation

Sample size calculation is based on a previous study of a similar population where patients had a mean QoL score at 0.57 (SD 0.17) [32]. A minimal clinical relevant improvement and between group difference is considered to be 0.10 [33]. A sample size of 40 in each group has an 80% power to detect a 0.10 mean difference between groups with a significance level (alpha) of 0.05 (two-tailed). The power calculation was carried out with StatMate ver. 2.0 (GraphPad Software, Inc., San Diego, CA, US). We expect a 20% attrition rate at follow-up, thus, 50 patients will be needed in each group.

Statistics

Baseline variables will be reported with descriptive statistics. Difference between randomized groups on primary outcomes will be assessed with Student's t-test. Secondary outcome will be assessed with appropriate tests, e.g., the weekly repeated measures will be analyzed with generalized estimating equation (GEE) to test for differences between groups.

3. The project plan, project management, organization and cooperation

Project group:

- Principle investigator and PhD supervisor: [name] PhD, Addiction Unit (ARA), Sørlandet Hospital HF (SSHF)
- Assistant supervisor: [name] MD/PhD: ARA, SSHF and University of Oslo
- Statistical supervisor: [name] PhD: Oslo Centre of Biostatistics and Epidemiology, Oslo University Hospital
- User representative: [name]
- Clinical neurofeedback specialist, [name], ARA, SSHF

Advisory board:

The advisory board consists of national and international specialists on neurofeedback and QEEG [34, 35]. In addition, we cooperate with a community based researcher who is our link to the local municipality [36].

- [name], Clinical Director, London Scientific Neurotherapy

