been systematically collected for clinical use using similar instruments to those proposed here. Thus, data collection for the study will follow already established routines at the clinic. Based on the pilot study and practice at the clinic, the number of participants needed for this study is realistically achievable during the course of the planned two-year inclusion period.

Project time frame

- April 2017: Apply for relevant permissions (e.g., ethical approval). Clinical trial registration. Apply for funding.
- Autumn 2017: After ethical approval has been obtained, implement the experimental study in lieu of the clinical practice at ARA. Data collection.
- Autumn 2017: Find qualified PhD candidate as soon as funding is secured. Qualified graduates (with master's degrees) are currently doing clinical work at ARA. They are expected to apply for the position and will be able to start at relatively short notice.
- January 2018 to December 2019: Continue the experimental study and data collection
- Spring 2018. Start writing the first article based on the naturalistic cohort consecutively admitted after the first pilot study.
- January to December 2020: Complete follow-up interviews.
- Spring 2020 – Spring 2021. Write up papers.
- Autumn 2021: Write summary of PhD thesis research. Submit PhD thesis.
- The post-doc will be positioned with a two-year delay to await the on-going data collection.

Budget

See online application.

4. Key perspectives and compliance with strategic documents

Compliance with strategic documents

The project is in agreement with the Norwegian government's pronounced aim of making treatment of substance use and mental health disorders priority areas. This is intended achieved partly by strengthening the diversity in and to improve the quality of the treatment offered, including developing new, knowledge-based intervention methods [43]. Government documents also emphasize the importance of user involvement both on an individual level and to guide research in the field.

Relevance and benefit to society

Recognizing substance use disorder as a chronic, relapsing mental disorder, the effective treatment approaches should address both its biological, physiological and psychological domain components. This complexity calls for an integrative approach, and over the past thirty years NF training has surfaced as a medication free adjunct therapy to conventional intervention modalities for this patient group.

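### The primary QoL-10 analysis is a t-test with no baseline term and no stated score; ANCOVA on baseline QoL-10 would be more precise under either reading once the baseline-to-outcome correlation exceeds about 0.12

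*Combined protocol and SAP*

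**What the plan says.** - **Primary test.** Statistics: "Difference between randomized groups on primary outcomes will be assessed with" a Student's t-test. Baseline variables appear in that section only as something to be described.
- **Baseline measurement.** Experimental design: "All participants will complete the inventory described below at the outset". That inventory includes QoL-10, the primary outcome.
- **Score to be compared.** Not stated. The hypothesis is worded as a level, "higher QoL at the end of treatment as well as at a 3- and 12-month follow-up". The design is described differently: "The proposed experimental study will have a two-group pre-post design". The sample size section says: "A minimal clinical relevant improvement and between group difference is considered to be 0.10".
- **Baseline adjustment.** The only one planned is for retention, under Approaches, hypotheses, and choice of method: "Drop-out rates will also be compared for the two groups, controlling for baseline demographic and severity variables".
- **Power.** Sample size calculation: "A sample size of 40 in each group has an 80% power to detect a 0.10 mean difference between groups", with SD 0.17 from a previous study, two-sided alpha 0.05, and 50 per group enrolled to allow for 20% attrition.

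**The concern.** QoL-10 is measured on everyone before treatment, and a patient's baseline score can be expected to predict the later one to some degree. A t-test on follow-up scores ignores that information, so with about 40 patients per group the confidence interval is wider than it needs to be. It also carries part of any chance baseline difference into the estimate. A t-test on change scores over-corrects for the same difference.

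Because the score is not named, two different t-tests fit the text. They have different power unless r = 0.5, and nothing in the plan prevents the choice from being made after the data are seen. The hypothesis also covers three time points without naming a primary one.

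**Working it through.** **Inputs from the Sample size calculation section.** Difference 0.10; SD 0.17; n = 40 analysed per group; two-sided alpha 0.05.

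**Assumptions.** The documents give no baseline-to-outcome correlation r for QoL-10, so a range is shown. The change-score figures also assume the same SD at baseline and follow-up. The comparison of ANCOVA with the follow-up t-test does not need equal SDs.

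**Step 1: the plan's own figure.** The standard error of the difference is 0.17 × √(2/40) = 0.0380, so the noncentrality is 0.10 / 0.0380 = 2.63 on 78 degrees of freedom. Noncentral-t power is 73.8% (74.9% by the normal approximation). For 80% power the t-test needs 47 per group (46 by the normal approximation). A one-sided test does not explain the stated figure either: it needs 36 per group. The attrition step is correct: 40 / 0.80 = 50.

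**Step 2: the SD that enters each analysis.**
- Follow-up t-test: 0.17, 78 df.
- Change-score t-test: 0.17 × √(2(1 − r)), 78 df.
- ANCOVA: 0.17 × √(1 − r²), variance multiplied by 1 + 1/(2n − 4) = 1 + 1/76 = 1.0132 for estimating the slope, 77 df.

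**Step 3: power at 40 per group.**

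| r | Follow-up t-test | Change-score t-test | ANCOVA |
|---|---|---|---|
| 0 | 73.8% | 45.1% | 73.3% |
| 0.2 | 73.8% | 53.8% | 75.0% |
| 0.3 | 73.8% | 59.3% | 77.2% |
| 0.4 | 73.8% | 66.0% | 80.4% |
| 0.5 | 73.8% | 73.8% | 84.6% |
| 0.6 | 73.8% | 82.8% | 89.7% |
| 0.7 | 73.8% | 91.8% | 95.1% |

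**Step 4: thresholds.**
- ANCOVA and the follow-up t-test have equal power at r = 0.115. With 50 analysed per group the break-even is about 0.10.
- The variance ratio of ANCOVA to change score is 1.0132 × (1 + r)/2, which is below 1 until r is about 0.97. ANCOVA is therefore better over the whole practical range.
- ANCOVA reaches 80% power at r = 0.389. The change-score t-test needs r = 0.57.

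**Step 5: precision.** The 95% CI half-width for the follow-up t-test is 1.991 × 0.0380 = 0.076. For ANCOVA it is 0.073, 0.070, 0.066 and 0.061 at r = 0.3, 0.4, 0.5 and 0.6.

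**Step 6: chance imbalance.** Take a baseline difference D of one standard error, 0.038. The follow-up estimate shifts by r × D: 0.011 at r = 0.3, 0.019 at r = 0.5, 0.027 at r = 0.7. The change-score estimate shifts by −(1 − r) × D, which is −0.019 at r = 0.5. That is about a fifth of the 0.10 target.

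**Step 7: simulation.** With 100,000 trials per value of r, all three methods had a mean estimate of 0.100 and type I error of 4.9 to 5.1%. Power at r = 0.5 was 73.6%, 73.6% and 84.5%, in agreement with the table.

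**The case against.** An unadjusted t-test on a randomized outcome is a legitimate analysis, and no bias has been shown. That stands, and it is why this is an improvement rather than the correction of an invalid method.

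The size of the benefit depends on a correlation that the documents do not give. Break-even at 0.12 means no gain at that point, and the gain is only 1.2 points of power at r = 0.2 and 3.4 points at r = 0.3. Baseline is separated from the outcome by a five-month intervention, and then by 3 and 12 further months, so a high r cannot be presumed at every visit. This also stands. It limits the expected gain but does not favour the t-test, because the most that can be lost is 0.5 points.

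The text leans towards follow-up scores: the hypothesis is about a level, the outcome is defined as QoL-10 itself, and the SD is cross-sectional. The low change-score figures therefore belong to the less likely reading, and they rest on equal SDs. Both points are fair. The score is still not stated anywhere, and ANCOVA's advantage over the follow-up t-test does not depend on that question.

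The power shortfall and the unnamed primary time point are separate from the missing covariate. They are included because the replacement sentence has to name a time point, and because a change of model changes the power statement.

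**Conclusion.** The point holds. The planned test is valid, but it leaves out a prognostic measurement that the trial already collects, and its analysis variable is not specified. Relative to a follow-up t-test at 40 per group, ANCOVA adds about 3 points of power at r = 0.3, 7 at r = 0.4 and 11 at r = 0.5, for a cost of 0.5 points at r = 0. This matters more than usual here, because the planned t-test has 74% power and so misses the plan's own 80% target. ANCOVA would meet that target with the same 40 patients only if r is at least about 0.39. The algebra is firm; the size of the gain in this trial depends on the unknown r. This should be changed.

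**What to change.** Replace the primary-analysis sentence in Statistics with wording such as:

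> The primary result is the between-group difference in QoL-10 at end of treatment, estimated by ANCOVA (linear regression) with treatment group and baseline QoL-10 as covariates, reported as the adjusted difference with 95% CI. The 3- and 12-month differences, from the same model, are secondary. An unadjusted t-test on end-of-treatment scores is supportive.

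End of treatment is suggested because the list of planned papers treats the 12-month results separately. If the sponsor prefers another time point, that one should be named. Clinic is not needed in the primary model, since the plan mentions no stratification by clinic.

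Correct the power sentence in Sample size calculation:

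> With 40 analysed per group the unadjusted t-test has 74% power. ANCOVA has 80% power if the baseline-to-outcome correlation is at least 0.39. The assumed correlation and its source are stated.

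Section 3 says that clinic data have "been systematically collected for clinical use using similar instruments to those proposed here". If those data include a QoL score, the sponsor could estimate r from them.

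**Cost.** Two edits to the text and no new data, as baseline QoL-10 is already planned for everyone. If r = 0, power falls from 73.8% to 73.3%, or to 72.7% if clinic is also added. If the sponsor wants to keep 80% power and r turns out lower, more patients are needed: 43 analysed per group at r = 0.3 (43 / 0.80 = 53.75, so 54 enrolled) or 47 at r = 0 (47 / 0.80 = 58.75, so 59 enrolled), against the planned 50. That shortfall exists under the present t-test too, and ANCOVA does not create it.

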been systematically collected for clinical use using similar instruments to those proposed here. Thus, data collection for the study will follow already established routines at the clinic. Based on the pilot study and practice at the clinic, the number of participants needed for this study is realistically achievable during the course of the planned two-year inclusion period.

Project time frame

- April 2017: Apply for relevant permissions (e.g., ethical approval). Clinical trial registration. Apply for funding.
- Autumn 2017: After ethical approval has been obtained, implement the experimental study in lieu of the clinical practice at ARA. Data collection.
- Autumn 2017: Find qualified PhD candidate as soon as funding is secured. Qualified graduates (with master's degrees) are currently doing clinical work at ARA. They are expected to apply for the position and will be able to start at relatively short notice.
- January 2018 to December 2019: Continue the experimental study and data collection
- Spring 2018. Start writing the first article based on the naturalistic cohort consecutively admitted after the first pilot study.
- January to December 2020: Complete follow-up interviews.
- Spring 2020 – Spring 2021. Write up papers.
- Autumn 2021: Write summary of PhD thesis research. Submit PhD thesis.
- The post-doc will be positioned with a two-year delay to await the on-going data collection.

Budget

See online application.

4. Key perspectives and compliance with strategic documents

Compliance with strategic documents

The project is in agreement with the Norwegian government's pronounced aim of making treatment of substance use and mental health disorders priority areas. This is intended achieved partly by strengthening the diversity in and to improve the quality of the treatment offered, including developing new, knowledge-based intervention methods [43]. Government documents also emphasize the importance of user involvement both on an individual level and to guide research in the field.

Relevance and benefit to society

Recognizing substance use disorder as a chronic, relapsing mental disorder, the effective treatment approaches should address both its biological, physiological and psychological domain components. This complexity calls for an integrative approach, and over the past thirty years NF training has surfaced as a medication free adjunct therapy to conventional intervention modalities for this patient group.

Preliminary clinical experience indicates that the method represents an intriguing, technology-intensive option and a refreshing alternative for a treatment-fatigued patient population, resulting from offering traditional "talk therapies" only. The proposed study will provide new knowledge about the use of neurofeedback in the treatment of SUD, specifically the novel infra-low training methods, potentially leading to a more holistic treatment approach, improved retention and relapse rates, and reduced detrimental outcomes for a vulnerable and difficult to treat group of patients.

Environmental impact

The study is not expected to constitute any additional hazard to the environment.

Ethical perspectives

Participants will be included after they have provided written informed consent to join the study. Approval has been sought from the Regional Ethics Committee. Based on six years of clinical experience and the outcome of the 2012 pilot study, no adverse side effects are expected for the patients. In order to secure equal treatment to all participants, the TAU group will be offered NF after

study completion. The project group has decided against including a placebo control in the study, as the practice of offering 20 sessions of non-active feedback was deemed unethical.

Gender issues

Participants of both genders will be included, and it is expected that the sample will mirror the typical gender distribution of patients referred to addiction treatment. A female clinician with a master's degree will be engaged as clinical coordinator for the study and will be the natural candidate for the doctoral research fellowship position.

Dissemination and communication of results

At least six scientific papers are planned to be written, three of which will form the basis for a PhD dissertation, and three for the post-doc position. All are intended to be published in international peer-reviewed journals, such as *Substance Abuse Treatment, Prevention, and Policy*; *Addiction Science & Clinical Practice*; *Journal of Psychiatry and Neuroscience*, and *Applied Psychophysiology and Biofeedback*. The results will also be communicated in relevant national and international research arenas and targeted to decision makers in the addiction and health fields, as well as to the existing clinical network and their associated websites and social media sites. Moreover, the results will be used to expand and improve the practice of neurofeedback for the addiction population by providing further documentation of its effectiveness.

Tentative titles for the papers are as follows:

1. "Feasibility and effectiveness of neurofeedback in substance use treatment: Experiences from a naturalistic pilot study"
2. "Clinical effectiveness of neurofeedback in a mixed substance abuse population as measured by quality of life. A randomized controlled trial"
3. "Do effects last? Follow-up results 12 months after completing a neurofeedback intervention program for substance use disorders"
4. "Can neurofeedback reduce psychological distress in patients with substance use disorders? Secondary outcomes of an RCT."
5. "Does cognitive function predict effectiveness of and treatment retention in a neurofeedback treatment regime?"
6. "Hangin' in there: Can neurofeedback reduce drop-out rates and prevent relapse in addiction treatment? Assessment of costs and benefits."

Communication with users

Cooperation has been established with a user representative who has partaken actively in the entire research process. From an early phase, the representative has been instrumental in bringing in the user perspective in preliminary considerations, commenting on relevant questionnaires, thereby securing more useful outcome measures for the project. During the data collection phase, she will aid in the recruitment process and constitute a link to the research participants by taking part in patient interviews and screenings, encouraging their participation in the project, and highlighting its significance for the user population, both directly and through user organizations. Specifically, she is intended to play an active role in pre-treatment information and dialogue sessions, to which the NF-TAU participants are invited to discuss the program and ask any questions they may have concerning the intervention. She is also intended to aid in distribution of the results in relevant user forums in order to raise awareness of the method and its application for the SUD population. External user organizations will also play a part toward this end.

5. Additional information specifically requested in the call for proposals

A patient with a SUD is typically a frequent user of local health care services across his or her lifespan, and in comparison, the time spent in specialist treatment facilities is relatively short. A close cooperation between the services, both on a clinical level and with a view to research, is therefore paramount to treatment success with this patient group, and to secure life-long healing and QoL for the individual. In line with the Government's Coordination reform intentions, the neurofeedback intervention can be viewed as a potential addition to the support yielded at the municipal level,

reducing the need for these services and further strengthening the cooperation between the service providers[44]. Experience from the pilot study indicates that neurofeedback is welcomed by our local cooperating partners as a method for enhancing the function of their clients, and may thus serve as an additional useful tool in the continuum of care of the individual.

References

1. Hordvin O: **The Drug Situation in Norway 2011. Annual report to the European Monitoring Centre for Drugs and Drug Addiction – EMCDDA.** Oslo: Norwegian Institute for Alcohol and Drug Research.; 2011.

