1. One of the challenges with a technology-driven intervention method such as NF is that research often lags behind the rapid technological development. Whereas most of the studies to date have utilized NF treatment protocols based on measuring subsets of the EEG activity, divided into band rangebandrange frequencies in the 4-30 Hz specter (such as Theta, Alpha, Beta rhythms), current clinical interest in some milieus has shifted to slow cortical potentials (SCP). SCPs are slow, event-related, direct-current shifts in the EEG, originating from the large cell assemblies in the upper cortical layer in the midline of the brain [17]. Newer software and hardware technologies have made it possible to isolate and process even slower bandwidths, so-called infra-low frequency training (ILF), i.e. frequencies below 0.1 Hz. This particular form of NF training seems to have the potential to influence the brain's resting state networks, which is thought to have a central role in underpinning overall brain function [18]. ILF training can thus be said to target core regulatory function of the central nervous system, rather than remediating specific deficits or diagnoses. This can explain the claimed wide applicability of the method across diagnoses and symptom categories. However, although favorably received in some clinical communities, the empirical support for the claims for ILF training is as of yet virtually non-existent. It is therefore important to fill this

apparent gap in the literature.

2. This study is among the few in the addiction treatment field that has QoL as its main outcome measure. The rationale behind this choice of outcome is that improvement of QoL can be viewed as an overarching aim of addiction treatment, a generic expression of the patient's global functioning and well-being. A high QoL has been found to correlate with positive affect, and can thus help maintain the motivation to stay sober. Nevertheless, in previous studies QoL is rarely assessed; reduction in substance use has been given main focus. If living without substance use is to be the goal for the SUD patient, this aim will simply not be perceived as "worth" striving towards if it is not associated with improved well-being in at least some facets of life. Consequently, patients may lose motivation and interest in their rehabilitative process [19].

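### The plan expects no side effects and sets out no systematic adverse-event recording in either arm, so discrete harms would go uncounted

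*Combined protocol and SAP*

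**What the plan says.** Section 4, Ethical perspectives, gives the plan's only safety statement: "Based on six years of clinical experience and the outcome of the 2012 pilot study", "no adverse side effects are expected for the patients". No event counts or denominators accompany it.

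Side effects appear in one other place. The fourth listed departure from previous research (section 2, background) describes meetings between user representatives and participants, "allowing informal exchanges about the method (e.g., possible effects and side-effects". Experimental design and Communication with users offer these sessions to the neurofeedback (NF) arm. Nothing is said about recording what is raised there.

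Three statements set the context:
- On ILF training, the first listed departure says that "the empirical support for the claims for ILF training is as of yet virtually non-existent".
- Relevance and benefit to society describes a "vulnerable and difficult to treat group of patients".
- The exclusion criteria cover "Severe psychiatric disorders (e.g. psychosis) that have not been stabilized", so patients with stabilised disorders may enter.

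Exposure is "20 sessions of symptom-based NF tailored to the individual patient". Dissemination and communication of results says the findings will be used to widen the practice.

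**The concern.** A randomised comparison with a concurrent control arm is a good opportunity to collect harm data that can be interpreted. The instrument list is detailed, but in the available text it has no adverse-event definition, item or form. The Statistics section has no safety analysis, and none of the six tentative paper titles concerns harms.

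Discrete events that nobody asks about cannot be recovered at analysis. The trial could then report on effectiveness and support wider use, with no estimate of how often patients had a headache, a crisis, an admission or an episode of self-harm during or after the sessions. Nor could its results be used to check the expectation stated under Ethical perspectives.

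**Working it through.** **What the planned data could and could not show**

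| Possible harm | Planned measure (Instruments; Approaches, hypotheses) | Visible? |
|---|---|---|
| Worse sleep | 10 cm VAS | Yes, as an average |
| Restlessness, agitation | 10 cm VAS | Yes, as an average |
| Anxiety, depression | SCL-10 | Yes, as an average |
| More substance use | VAS, selected EuropASI items | Yes, as an average |
| Lower quality of life or functioning | QoL-10, ORS | Yes, as an average |
| Leaving treatment | Drop-out compared by arm | Yes, but no recording of reasons is described |
| Craving | No dedicated item listed | Not directly |
| Headache, psychiatric crisis, admission, self-harm | No item listed | No |

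The EuropASI items are an unlisted selection placed under substance use, so they cannot be assumed to cover the last row.

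The scales are planned as efficacy outcomes, with no rule for individual deterioration. An illustration with assumed figures shows why means can hide harm: if 5% of NF patients worsen by 3 cm on a 10 cm scale, the arm mean moves by 0.05 × 3 = 0.15 cm.

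**What recording would buy**

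The plan states no safety figure, so there is none to reproduce. The denominators come from the Sample size calculation: 50 enrolled per arm, and 50 × (1 − 0.20) = 40 after the expected attrition. They serve here only as denominators. All event rates below are assumptions, because the documents give none.

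Probability of at least one case among n patients at true incidence p is 1 − (1 − p)^n:
- n = 50: p = 5% gives 1 − 0.95^50 = 0.923; p = 2% gives 1 − 0.98^50 = 0.636; p = 1% gives 0.395.
- n = 40: p = 5% gives 1 − 0.95^40 = 0.871; p = 2% gives 1 − 0.98^40 = 0.554; p = 1% gives 0.331.

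Exact one-sided 95% upper limit with zero events is 1 − 0.05^(1/n):
- n = 50: 0.058; n = 40: 0.072.
- The two-sided 95% version, 1 − 0.025^(1/n), gives 0.071 and 0.088.

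Power to compare arms, two-sided alpha 0.05, normal approximation, is Φ{[|p2 − p1| − 1.96 √(2p̄(1 − p̄)/n)] / √[(p1(1 − p1) + p2(1 − p2))/n]}. For 5% in controls against 10% in NF with n = 50, p̄ = 0.075 and this is Φ{(0.05 − 1.96 × 0.0527)/0.0524} = 0.155.

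| Control vs NF rate (assumed) | 50 per arm | 40 per arm |
|---|---|---|
| 5% vs 10% | 15% | 13% |
| 5% vs 15% | 38% | 32% |
| 5% vs 20% | 62% | 53% |
| 5% vs 25% | 81% | 71% |

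The trial would therefore describe and bound common harms. It would not reliably separate the arms unless the difference were large.

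**The case against.** The strongest reply is that the plan already looks where harm is most plausible. Sleep, restlessness, distress, substance use and quality of life are measured, participants are reassessed after treatment and at 3 and 12 months, and follow-up interviewers are blinded. Drop-out is compared, and non-completers are to be examined. This stands. A reader might infer that the trial cannot detect harm at all, or that worse sleep or agitation would go unrecorded. The documents do not support that: average worsening and excess drop-out could be seen.

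Three other inferences also go too far:
- That the plan calls its whole method untested. The remark on missing support concerns the claims for ILF training and is not a statement about safety. The background cites a review rating alpha-theta training favourably and reports use at the clinic since 2011.
- That side effects are assumed away. The plan says none are expected, and elsewhere it acknowledges that they are possible.
- That talks with the user representative are the only channel. No section says so. Patients also meet clinicians and interviewers, although no recording of adverse events is described for those contacts either.

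Part of section 3 is missing from the available text, so a procedure described there cannot be ruled out.

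**Conclusion.** The concern holds in a limited form. In the available text, neither arm has systematic adverse-event recording or reporting. The outcome scales and drop-out give indirect, averaged signals of harm; discrete events and craving would not be counted.

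Systematic recording would replace no incidence estimate with a modest one. A harm with 5% incidence would be seen at least once with 92% probability in 50 NF patients, or 87% in 40, and zero events would bound incidence below 5.8% or 7.2% respectively. These figures rest on assumed rates, independent patients, and every affected patient reporting the event when asked. Zero events would not show safety, and one observed case would not establish cause. This is a worthwhile, cheap improvement; it does not threaten the primary comparison.

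**What to change.** Define adverse events in the protocol. Add the same short item set for both arms to the post-treatment, 3- and 12-month assessments: new or worse symptoms (headache, sleep, agitation, mood, craving), any other event, and serious events, with a stated recall period. Word the items without reference to neurofeedback, so that asking them does not unblind the interviewers. Report counts of patients with events by arm, with exact confidence limits, and state that zero events does not demonstrate safety.

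Add the items to the weekly computer test only once it is confirmed that both arms complete it. The Instruments text is ambiguous: the test is introduced as a way to follow change in the NF arm, yet "a simple computer-based screening test will be administered weekly to each participant during the project period", and the Statistics section plans between-group tests on the weekly measures. Collection in the NF arm alone would give unequal ascertainment.

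The cost is slightly longer questionnaires and one extra table. Attaching the items to the three planned assessments needs no new visits. The trade-off is that recall over months may miss brief effects.
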